#### 7.6.3 Medication

Subjects will be instructed not to take any prescription medications within two weeks prior to check-in and throughout the study. Subjects will be instructed not to take any OTC products, herbal medications, etc. within one week prior to check-in and throughout the study. If these medications are required, subject will not be enrolled or may be withdrawn from study by investigator.

#### 7.6.4 Others

Subjects will be instructed to refrain from pan or pan masala, gutkha, masala (containing beetle nut and tobacco) for 48.00 hours prior to check-in to till check-out/last sample of the study.

Protocol for Drug-Drug Interaction Study of Spironolactone and Digoxin (Fasting Condition) Confidential

#### 8 **BIOANALYTICAL PROCEDURES**

#### 8.1 Method Description

- a. The bioanalytical method will be developed & validated by using LC-MS/MS for quantification of digoxin in presence of spironolactone and canrenone as per current version of in-house SOP "Bioanalytical Method Validation" and applicable regulatory requirements.
- b. Samples will be assayed for digoxin in presence of spironolactone and canrenone using the validated method at ClinSync Clinical Research Pvt. Ltd., Hyderabad.
- c. Unchanged drug excreted in urine for digoxin will be analyzed by using validated LC-MS/MS method.
- d. Analysis of the plasma will include distribution of quality control samples throughout each batch of study samples. All the available plasma samples will be analyzed in bio-analytical laboratory.
- e. However, the samples of all withdrawn and dropped out subjects will be analyzed and tabulated in a separate table.
- f. The analyst will not have access to the randomization code list during the course of the analysis.
- g. All concentration values below the limit of quantification (BLQ) will be set to zero for obtaining descriptive statistics. All zero pre-dose concentrations will not be reported as BLQ
- h. Whenever possible, all samples from each subject will be analyzed on the same standard curve. Samples with drug concentration greater than the upper limit of the validated range of the assay will be diluted with the appropriate drug-free biological fluid and method validation and repeat analysis will be done as per the current version of applicable ClinSync SOP.
- i. Incurred sample reanalysis (ISR) will be performed as per current version of applicable ClinSync SOP.

#### 9 PHARMACOKINETIC ASSESSMENTS

Concentration data of subjects versus time, which are received after analysis of samples, will be included in the final data analysis. Data from subjects with

VASAVIINSTITUTIONAL ETHIGEGINNITEEMP-S APPROVED

Protocol for Drug-Drug Interaction Study of Spironolactone and Digoxin (Fasting Condition) Confidential

missing concentration values (missed blood samples, lost samples, samples unable to be quantified) may be used if pharmacokinetic parameters can be estimated using remaining data points, otherwise data from these subjects will be excluded from the final analysis.

All concentration values below the limit of quantification (BLQ) will be set to zero for all pharmacokinetic and statistical calculations. Any missing samples will be reported as 'Missing' and will be denoted as "M" while running pharmacokinetic and statistical analysis.

The following pharmacokinetic parameters will be computed using noncompartmental model of Phoenix WinNonlin Professional Software Version 6.4 (Pharsight Corporation, USA) or above.

Pharmacokinetic Parameters for digoxin in plasma:

Primary Pharmacokinetic parameters

C max	:	Maximum measured plasma concentration.						
		Area under the plasma concentration versus time curve						
AUC 0-96	:	from time 0 to the 96 hour time point concentration,						
		calculated by linear trapezoidal method.						

Secondary Pharmacokinetic parameters

Time to achieve maximum plasma concentration. If the
 Tmax : maximum value occurs at more than one time point, Tmax is defined as the first time point with this value.

Pharmacokinetic Parameters for digoxin in urine:

CLR: Renal clearance Ae0-240h/AUC0-240h

fc: Unchanged drug excreted in urine

For all the above computations, actual time points of the sample collection will be used in case of sample collection deviations.

In clinical phase or sample analysis process, if 3 or more consecutive post dose samples for any subject are found to be missing, samples of such subjects will be analyzed but pharmacokinetic data of those subjects will be excluded from the final statistical analysis.

### & ClinSync

Protocol for Drug-Drug Interaction Study of Spironolactone and Digoxin (Fasting Condition) Confidential

Pharmacokinetic data of those subjects will be tabulated and reported in the study report as a separate table. However, the data of such subjects will also be considered for statistical analysis if the 3 consecutive post dose samples are the last three samples of elimination phase.

If the pre-dose concentration appears to be > 5% of the  $C_{max}$  in any subject at any period, the data of such a subject will be excluded from the statistical analysis.

#### 10 STATISTICAL ANALYSIS

Statistical analysis will be performed by using SAS statistical software version 9.3 or above.

Descriptive statistics of all the pharmacokinetic parameters will be computed and reported for digoxin.

#### 10.1 Number of subjects

A total number of 28 healthy adult human subjects will be enrolled in the study. Additionally, 04 stand-by subjects will be included in order to dose 28 subjects in period I. As the same perpetrator (LANOXIN® Tablets USP 250 mcg) will be given to both the treatments and only the difference is going to be with and without spironolactone oral suspension, 28 subjects along with 04 stand-by subjects will be sufficient to provide a reliable estimate of the magnitude and variability of the interaction.

#### 10.2 Analysis of variance

The log-transformed pharmacokinetic parameters (Cmax and AUC0-96) will be analyzed using Type III sum of squares, with the main effects of formulation, period, sequence and subjects nested within sequence as random effect. A separate ANOVA model will be used to analyze each of the parameters. The sequence effect will be tested at the 10% level of significance using the subjects nested within sequence mean square as the error term. Formulation and period effects will be tested at the 5% level of significance against the residual error (mean square error) from the ANOVA model as the error term. Each analysis of variance will include calculation of least-squares means, the difference between the adjusted formulation means and the standard error associated with the difference.

Protocol for Drug-Drug Interaction Study of Spironolactone and Digoxin (Fasting Condition) Confidential

#### 10.3 Two one-sided test for bioequivalence

Two one-sided test (Schuirmann's test, 1987) for bioequivalence and 90% confidence intervals for the ratio of least squares mean between drug formulations will be calculated, for ln-transformed data of  $C_{max}$  and  $AUC_{0.96}$ .

#### 10.4 Power

The power of a test to detect 20% difference between treatment A & B will be computed and reported.

#### 10.5 Ratio analysis

The comparison of interest is Treatment (A) Vs Treatment (B), so the ratios will be of the form: Treatment (A/B).

Ratio of least squares means of Treatment A & B will be computed for Intransformed pharmacokinetic parameters  $C_{max}$  and AUC0.96. Ratio analysis will be reported in percentage for In-transformed pharmacokinetic parameters ( $C_{max}$  and AUC0.96) for Digoxin.

#### 10.6 Intra-Subject Variability

Intra-Subject variability will be computed for In-transformed pharmacokinetic parameters ( $C_{max}$  and AUC0-96) for Digoxin.

#### 10.7 Criteria for evaluation

The presence or absence of DDI between two treatments (A and B) will be based on the statistical results of 90% confidence interval for the ratio of the geometric least squares mean for log-transformed pharmacokinetic parameters  $C_{max}$  and AUC0-96 for Digoxin.

Absence of drug-drug interaction will be established if the 90% CI for the ratio of population geometric means between two treatments (A and B), based on log-transformed data, present in the equivalence limits of 80.00 - 125.00% for Cmax and AUC0-96.

Summary statistics of pharmacokinetic profile of Digoxin (substrate drug) in the presence and absence of spironolactone (perpetrator) will be provided based on plasma and urine data. Renal clearance (CLR)/ Percent Recovered and unchanged drug excreted in urine ( $f_e$ )/Amount Recovered for Digoxin will also be measured

Protocol for Drug-Drug Interaction Study of Spironolactone and Digoxin (Fasting Condition) Confidential

#### 11 ASSESSMENT OF SAFETY

#### 11.1 Specification of Safety Parameters

Vital signs (seated blood pressure, radial pulse rate and oral/aural temperature) will be measured as per section 11.2.

#### 11.2 Methods and Timing for Assessing, Recording and Analyzing Safety Parameters

Clinical examination along with vital signs (seated blood pressure, radial pulse rate and oral/aural temperature) measurement will be carried out and recorded at check-in and at checkout of each period and/or at the termination of the study.

Clinical examination will be carried on prior to dosing on day 06 in each study period.

Oral/aural temperature will be measured prior to dosing.

Vital parameters – seated blood pressure and radial pulse rate will be measured at prior to dosing, 1.00, 3.00, 5.00 and 11.00 hours post dose in each period from Day 1 to Day 5, whereas from Day 6 to Day 9, vitals will be measured at prior to dosing, 1.00, 2.00, 3.00, 5.00, 8.00 and 11.00 hours post dose in each period. A window period of  $\pm$  45 minutes from the scheduled time point is allowed for post dose vitals recording.

#### ECG Measurements:

- ECG will be performed before period II check in and subject study eligibility will be assessed as per the principal investigator discretion.
- ECG will be performed at 1.00 and 3.00 hours post dose in each period on Day 6 with a window period of ± 45 minutes from schedule time.
- ECG will be performed at check-out of each period of the study.

Note:

- On Day 6 the Vital sings (i.e. up to 3.00 hours post dose) will be performed at bed side only.
- 2D echo will be performed at the time of screening.
- Dosing will be done under the supervision of cardiologist.
- For subjects who are randomized to treatment A, the vitals will be checked at 5.00 hours post dose during day 1 to Day 5. However, the vitals time points

Page 55 of 83

Protocol for Drug-Drug Interaction Study of Spironolactone and Digoxin (Fasting Condition) Confidential

will be similar from day 6 for treatment groups A and B.

Vital signs may also be carried out at any time during the conduct of the study if the attending physician feels it necessary. In case of abnormality in vital signs during pre-dose vitals, recording, medical opinion will be taken whether to dose the subject or not.

#### Additional Laboratory evaluations (Biochemistry):

In each study period creatinine clearance and serum potassium levels to be measured on day 05 and the dosing eligibility of the subjects will be done as per the principal investigator discretion.

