## (Fasting Condition)

	Geometric Least Square Means and It's Ratio						1
PK Parameters (Unit)	Treatment A	Treatm	ent B	(Treatment A / Treatment B) (%)	ISCV (%)	90% Cl	Power (%)
LOG C max (ng/mL)	1456.085	2254.	.118	64.597	40.07	54.18% to 77.02%	67.47
LOG AUC 0-96 (ng.hr/mL)	13473.043	15996	5.644	84.224	18.56	77.45% to 91.59%	99.56
able 4: Summ	ary of Urine P	harmaco		tic parameters fo	or digoxin	– Treatment (A	4)
Treatment	Product/S	tatistics		enal clearance CLR)/Percent Recovered	unchanged drug excreted in urine (fe)/ Amount Recovered		
	N	N		28		28	
	Mean			54.687		136717.72	
	SD		_	29.158		72895.492	
Treatment A	Min			22.180		55449.800	
Heatment A	Median			46.111		115277.98	
	Max			147.642		369104.30	
	G. Mean			49.042		122606.02	
	G.mean 9	G.mean %CV		48.257		48.257	
able 5: Summa	ary of Urine Pl	harmacc	okinet	ic parameters fo	r digoxin	– Treatment (I	3)
Treatment	Product/S	tatistics		enal clearance CLR)/Percent Recovered		anged drug excr (fe)/ Amount Re	
	N			28		28	
		1					

	IN IN	20	20
	Mean	53.378	133446.07
	SD	21.256	53141.044
Tractment D	Min	21.641	54103.200
Treatment B	Median	51.185	127962.08
	Max	95.602	239003.90
	G. Mean	49.410	123523.87
	G.mean %CV	42.201	42.201

Safety Results	There were no adverse events recorded during the study.			
	Therefore, the safety of the digoxin in the presence and absence of spironolactone would be considered as comparable.			

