### Electrolyte and Metabolic Abnormalities

In addition to causing hyperkalemia, Spironolactone Oral Suspension can cause hyponatremia, hypomagnesemia, hypocalcemia, hypochloremic alkalosis, and hyperglycemia. Asymptomatic hyperuricemia can occur and rarely gout is precipitated. Monitor serum electrolytes, uric acid and blood glucose periodically. *Gynecomastia* 

Spironolactone Oral Suspension can cause gynecomastia. In RALES, patients with heart failure treated with a mean dose of 26 mg of spironolactone once daily, about 9% of the male subjects developed gynecomastia. The risk of gynecomastia increases in a dose-dependent manner with an onset that varies widely from 1-2 months to over a year. Gynecomastia is usually reversible.

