Blood tests:		Urine analysis
Hematology	Biochemistry	Office analysis
Hemoglobin	Random blood glucose	Physical Examination
Total RBC Count	Blood urea	Chemical Examination
Total WBC Count	Serum creatinine	Microscopic examination
Platelet count	Serum uric acid	
Differential count	Serum sodium	
Peripheral smear	Serum potassium	
Blood group	Serum chloride	
ESR	Serum calcium	
	Serum magnesium	
Serology:	Liver Function Tests:	
HIV (1 & 2)	Total Bilirubin	
antibodies	Direct Bilirubin	
HBsAg (Hepatitis	SGOT (AST)	
Bsurface antigen)	SGPT (ALT)	
Anti-hepatitis C	Alkaline phosphatase	
Virus (HCV)	Total proteins	
VDRL (RPR)	Albumin	
	Total Cholesterol	

Laboratory evaluations performed during screening are as follows:

Note: The laboratory parameters will be evaluated as per laboratory reference ranges (Appendix-IV). In rare instances, when the values are out of laboratory

Protocol for Drug-Drug Interaction Study of Spironolactone and Digoxin (Fasting Condition) Confidential

reference ranges, then those values will be correlated with clinical condition of the subject for further evaluation.

Laboratory (safety) evaluations performed at the end of study:

About 07 mL of blood will be collected from each subject for safety evaluation [which includes hematology (except blood group and Rh typing) and biochemistry (except random blood sugar) as per section 11.2] at the end of the study. If the subject does not come for the safety evaluation on scheduled time for any reason, follow-up will be done as per applicable Clinsync SOP.

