#### **Recording of Adverse events**

All adverse events including both observed and volunteered ones will be recorded on the appropriate AE form (As per applicable Clinsync SOP), irrespective of its association with the investigational products. Laboratory parameters, which are outside the clinically acceptable ranges but are not clinically significant as per PI discretion, must be recorded in the lab report and respective CRF page as Nil Significant. Clinically significant abnormal laboratory values that represent a change from baseline should be recorded diagnostically as AE's (e.g.: for elevated serum glucose, the AE would be described diagnostically as "hyperglycemia"). Determination of Clinical significance is based on the Investigator's medical judgment/discretion. PI shall evaluate the event for its severity, causality and seriousness that require immediate report to IEC and sponsor.

The institutional ethics committee (IEC), regulatory agency (ies), and the sponsor will be informed regarding the adverse events as necessary. Any serious adverse events will be recorded in appropriate Serious Adverse Event Reporting Form (As per applicable Clinsync SOP).

The investigator shall report all serious and unexpected adverse events to the licensing authority, the sponsor or his representative, whosever had obtained permission from the licensing authority for the conduct of the study and the ethics committee that accorded approval to the study protocol, within twenty-four hours of their occurrence. In case the Investigator fails to report any serious adverse event within the stipulated period, he shall have to furnish the reason for the delay

Protocol for Drug-Drug Interaction Study of Spironolactone and Digoxin (Fasting Condition) Confidential

to the satisfaction of the Licensing Authority along with the report of the serious adverse event. The report of the serious adverse event, after due analysis shall be forwarded by the investigator to the Licensing Authority, chairman of the Ethics Committee and the Head of the Institution where the trial has been conducted within fourteen calendar days of the occurrence of the serious adverse event.

Serious adverse events report submitted to Licensing Authority will be in color coded binding, where the reports of SAEs of Deaths are submitted in red cover, the report of SAEs of injury other than deaths in blue cover and the remaining cases of SAE report in white cover.

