#### 15.1 Study Report and Documents

The final report format will be prepared as per ICH E3: Structure and Content of Clinical Study Reports and as per CDSCO regulatory requirements. Supplementary Documents such as screening records, Period I and Period II records etc. will be given along with study report. Frequency distributions of gender and race will be tabulated by treatment and sequence. Summary statistics for age, body weight, height, and Body Mass Index (BMI) will be tabulated by treatment sequence. Listings of pre study & post study laboratory values, listing of adverse event by subject, listing of urine drug scan by subject, listings of protocol deviations, summary of adverse events by organ class will be provided in clinical phase of CSR.

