#### Appendix II: Assessment schedule

The following time-and-events table illustrates the planned schedule of assessments:

\*Chest X-Ray (P/A view) will be taken for the volunteer whose X-Ray was taken more than 6 months

VASAV: INSTITUTIONAL Period I.

	MONTE CONTRACT OF TOTAL	1
Bernin I	ETHICS COMMITTEE	[
Pictures.		P_SP
2010	APProtocol-No.;ED	-011
ž	METRUVEL	

Protocol for Drug-Drug Interaction Study of Spironolactone and Digoxin (Fasting Condition) Confidential

\* ECG will be performed at 1.00 and 3.00 hours post dose in each period of the study and before check in of period-II & before checkout of each period.

\$ Spironolactone Oral Suspension will be administered from Day 1 to Day 5 and Day 7 to Day 9, to the subjects who will be randomized to treatment B as per randomization scheme and treatment A or B will be administered on day 6.

The day prior to drug administration in each period for this protocol will be considered as Day '-1'.

The day of dosing in each period for this protocol will be considered as Day 1.

-  Post study (hematology and biochemistry) laboratory evaluations will be done at last blood sample collection of the study.
-  Serum pregnancy test will be done for female subjects with child bearing potential and Urine pregnancy test will be done for post-menopausal female subjects during screening, each period check-in (Day '-1').
-  Evaluation of inclusion/exclusion criteria will be carried out prior to check-in of period I of the study.
-  Investigational products (substrate) will be dispensed a day before dosing and perpetrator will be dispensed on the day of dosing in each period of the study.

Condition)	Confidential

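### The Day 5 safety sample omits sodium, so the 14 subjects in sequence BA have no scheduled sodium value while taking spironolactone

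*Protocol*

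**What the plan says.** **During dosing.** Protocol section 11.2 (additional laboratory evaluations) states: "In each study period creatinine clearance and serum potassium levels to be measured on day 05". The investigator uses those results to judge whether a subject may be dosed on Day 6. The blood budget in section 6.5 and the schedule in Appendix II show the same two tests, and the study report (section 12.5) describes them as done.

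**Before and after.** Serum sodium is in the screening biochemistry list in section 11.2. That biochemistry, without random glucose, is repeated once. A footnote to Appendix II fixes the time: "Post study (hematology and biochemistry) laboratory evaluations will be done at last blood sample collection of the study".

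**The risk.** Section 2.1.7 warns that "Spironolactone Oral Suspension can cause hyponatremia", among other electrolyte disturbances, and advises: "Monitor serum electrolytes, uric acid and blood glucose periodically". Section 2.1.6 also lists hyponatremia as an adverse reaction.

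**How laboratory findings reach the safety data.** Section 11.3 says: "Clinically significant abnormal laboratory values that represent a change from baseline should be recorded diagnostically as AE's". Out-of-range values that the investigator judges not clinically significant are noted in the laboratory report and case report form instead. Section 15.1 plans this laboratory output: "Listings of pre study & post study laboratory values". The SAP does not deal with laboratory safety data.

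**The concern.** In a two-period crossover, a single end-of-study panel falls at a different point relative to the perpetrator drug in each sequence. AB subjects have just finished Treatment B. BA subjects have just finished Treatment A and left spironolactone behind in Period I. The Day 5 sample could have closed that gap, because it is drawn in both periods, but it does not include sodium.

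Both of the sodium values scheduled for a BA subject, at screening and at study end, are therefore off drug. A listing of pre-study and post-study values cannot show what happened to sodium during nine days of a drug that, by section 2.1.2, increases sodium and water excretion. At stake is whether a clinically significant but symptomless fall in half the subjects could be seen and recorded. The pharmacokinetic comparison is not involved.

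**Working it through.** **1. How many full panels are scheduled?** Section 6.5 itemises blood loss for a male subject:

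- pharmacokinetic samples: 50 × 5 mL = 250 mL
- discarded blood: 40 × 0.5 mL = 20 mL
- screening: 9 mL
- Day 5 creatinine clearance and potassium: 2 × 3 mL = 6 mL
- post-study safety: 7 mL

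250 + 20 + 9 + 6 + 7 = 292 mL, which reproduces the stated total. The budget holds one post-study panel. A second one, at the end of Period I, would make it 292 + 7 = 299 mL. The Day 10 biochemistry mark in Appendix II sits in a column shared by both periods, but the footnote and this budget confine it to Period II.

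**2. Who is on drug when sodium is measured?** Section 4.2 allocates equally to AB and BA, so 28 / 2 = 14 per sequence; report Table 9 confirms 14 and 14. Dose dates are from report section 9.4.1 and the last-sample date from the report synopsis. Section 2.1.3 gives half-lives of 10 to 35 hours for canrenone and two other metabolites.

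| Sequence | Last spironolactone dose | End-of-study sample | Gap | Gap in half-lives (35 h to 10 h) |
|---|---|---|---|---|
| AB (14) | 16 Apr 2019 | 17 Apr 2019 | about 1 day | 24/35 = 0.7 to 24/10 = 2.4 |
| BA (14) | 19 Mar 2019 | 17 Apr 2019 | 29 days | 696/35 = 19.9 to 696/10 = 69.6 |

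The AB value can fairly be counted as on drug, while the BA value is fully off drug. The plan gives the same gap without the dates: with period starts 28 days apart, Period II Day 10 is 28 + 1 = 29 days after Period I Day 9.

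**3. What can be compared?**

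- AB subjects: screening (off drug) against about one day after the ninth dose. This is an on/off pair within each subject, confounded with time.
- Between sequences at the last sample: 14 AB just off Treatment B against 14 BA just off Treatment A, a randomised comparison.
- Within a subject, spironolactone against Treatment A on the same study day: available for no one.
- BA subjects on drug: nothing scheduled.

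**4. Effect of adding sodium on Day 5.** Subjects with a scheduled on-spironolactone sodium rise from 14 of 28 to 28 of 28. Extra results: 28 subjects × 2 periods = 56. The Day 5 values would follow four or five doses, since the protocol does not say whether that blood is drawn before or after the day's dose. The existing AB values follow nine.

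**5. What stays uncovered.** BA subjects take 14 × 9 = 126 spironolactone doses. Those on Days 6 to 9 number 14 × 4 = 56, or 14 × 5 = 70 from Day 5 on if the blood is drawn before that day's dose. No scheduled sodium would follow these doses within the period.

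**The case against.** The best defence is that the Day 5 test has a different job. It decides whether digoxin may be given on Day 6, and section 2.2.7 names renal function, potassium, magnesium and calcium as bearing on digoxin toxicity, but not sodium. The subjects are healthy, aged 20 to 35, and housed throughout nine days of dosing, with vital signs, questioning about adverse events and round-the-clock medical cover. The monitoring advice in section 2.1.7 is product warning text with no stated interval.

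Much of this stands. It explains the choice of tests, means that symptomatic events would be noticed, and keeps the point small. It does not answer the spironolactone risk: the mitigation text in section 11.2 argues from a single digoxin dose and does not discuss the electrolyte effects of the nine-day perpetrator. Unscheduled testing remains possible, but an unmeasured sodium cannot prompt it.

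It is also fair that sodium is not unique. Magnesium, calcium and chloride have the same gap, and nothing here ranks sodium above them.

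Several stronger inferences are tempting and should not be drawn:

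- **That no subject has an on/off sodium pair.** AB subjects do, as shown in the working.
- **That any low value would have been an adverse event.** The definition in section 11.3 only allows an abnormal laboratory finding to be one; the recording rule requires clinical significance.
- **That the 4 to 5 litres of water a day in section 6.6 lowered sodium.** The documents do not show this, and the report mentions only free access to water.
- **That the report's safety conclusion is wrong.** It reads: "Therefore, the safety of the digoxin in the presence and absence of spironolactone would be considered as comparable". It is drawn from the absence of recorded adverse events and makes no statement about sodium. Nothing in the documents shows that a fall occurred.

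**Conclusion.** The omission is clear from the text. The 14 BA subjects have no scheduled sodium value on spironolactone, although the protocol names hyponatremia as a risk of the drug. The consequence is limited: a clinically significant fall without symptoms in one of these subjects would not be detected by the schedule. No primary endpoint and no drug-interaction conclusion depends on it.

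The size is best stated as a count, 14 of 28 subjects now and 28 of 28 with the change, taking a value about one day after the ninth dose as on drug. A reader might convert this into zero-event upper bounds of 19.3% for 14 subjects and 10.1% for 28 (one-sided 95%, 1 − 0.05^(1/n)). That treats the risk after four or five doses and after nine as one rate, which the documents do not support. They also give no expected rate or size of a sodium fall, so no detection probability can be derived from them. This is an inexpensive improvement worth considering, not a defect in the trial's main inference.

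**What to change.** In section 11.2, add serum sodium to the Day 5 sample already drawn in each period. The investigator reviews it with potassium and creatinine clearance before Day 6 dosing, under the discretion already given there. List the results by treatment, so that each subject's spironolactone value stands beside the same-day Treatment A value. Keep the end-of-study panel, which covers AB subjects after all nine doses. Make matching edits to section 6.5 and Appendix II.

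The cost is the 56 additional results and occasional follow-up of minor abnormalities. There is no new draw and the 292 mL total is unchanged, provided the 3 mL sample suffices, which the documents do not state. Days 6 to 9 in BA subjects remain uncovered. A full second panel at the end of Period I would address that, at 299 mL. As the study is complete, the edit serves a repeat study or a template.
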